- Endpoint: American College of Rheumatology (ACR) 20 at Week 12
- How to account for intercurrent events (ICEs): ICEs related to study intervention include the use of rescue or prohibited medication and early discontinuation (ED) from the study or study intervention. A composite strategy will be used for these types of ICEs. Specifically, participants with ICEs related to study intervention will be considered as treatment failure (having no change from baseline), that is, a nonresponder, after the first occurrence of these ICEs.
- Population-level summary: Difference in proportion of participants achieving response at Week 12 between each dosing regimen of peresolimab and placebo
- Rationale for estimand: The primary estimand strategy assumes that:

- o If a participant used any rescue or prohibited medication, the participant was not receiving sufficient benefits from study intervention.
- o If a participant early discontinued the study or study intervention, the participant experienced a burden of study intervention that outweighed its benefits.

Secondary estimand for categorical endpoints at Week 12

For secondary objectives that have categorical endpoints analyzed at Week 12, the clinical question of interest is:

What is the difference between peresolimab and placebo in the target patient population, in achieving a successful response at Week 12 without use of rescue or prohibited medications or discontinuing the study intervention?

The estimand is described by the following attributes:

- Population: Participants with moderately-to-severely active RA
- Endpoint(s): ACR50, ACR70, Disease Activity Score high-sensitivity C-reactive protein (DAS28-hsCRP) low disease activity (LDA), Disease Activity Score erythrocyte sedimentation rate (DAS28-ESR) LDA, Simplified Disease Activity Index (SDAI) LDA, Clinical Disease Activity Index (CDAI) LDA, DAS28-hsCRP remission, DAS28-ESR remission, SDAI remission, and CDAI remission at Week 12
- How to account for ICEs: ICEs will be accounted using the same estimand strategy as for the primary estimand.
- Population-level summary: Difference in proportion of participants achieving response at Week 12 between each dosing regimen of peresolimab and placebo
- Rationale for estimand: Refer to the rationale for the primary estimand.

Secondary estimand for continuous endpoints at Week 12

For secondary objectives that have continuous endpoints analyzed at Week 12, the clinical question of interest is:

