What is the difference between peresolimab and placebo in the target patient population, in average change from baseline to Week 12 if all participants continued with treatment for 12 weeks without use of rescue or prohibited medications?

The estimand is described by the following attributes:

- Population: Participants with moderately-to-severely active RA
- Endpoint(s): Change from baseline for DAS28-hsCRP, SDAI, CDAI, 68 tender joint count (TJC68), 66 swollen joint count (SJC66), Physician's Global Assessment of Disease Activity (visual analog scale [VAS]), Patient's Global Assessment of Disease Activity (VAS), Patient's Assessment of Arthritis Pain (VAS), patient's assessment of physical function using the Health Assessment Questionnaire Disability Index (HAQDI), the duration and severity of morning joint stiffness, and Functional Assessment of Chronic Illness Therapy-Fatigue (FACIT-F) scores at Week 12

- How to account for ICEs: ICEs related to study intervention include the use of rescue or prohibited medication and ED from the study or study intervention. A hypothetical strategy will be used for these types of ICEs. Specifically, data collected after the first occurrence of ICE related to study intervention will be excluded from an analysis, and what the treatment effect would have been if rescued or prohibited medication(s) was not used, and all patients adhered to the treatment for 12 weeks will be estimated.
- Population-level summary: Difference in mean change from baseline to Week 12 between intervention conditions
- Rationale for estimand: The data collected after the treatment discontinuation, or the use of rescue or prohibited medication will not present the true efficacy effects.

Secondary estimand for categorical endpoints at Week 24 and Week 60

For secondary objectives that have categorical endpoints analyzed at Week 24 (or Week 60), the clinical question of interest is:

What is the proportion of achieving a successful response at Week 24 (or Week 60) in the target patient population without use of rescue or prohibited medications or discontinuing the study intervention?

The estimand is described by the following attributes:

- Population: Participants with moderately-to-severely active RA
- Endpoint(s): ACR20, ACR50, ACR70, DAS28-hsCRP LDA, DAS28-ESR LDA, SDAI LDA, CDAI LDA, DAS28-hsCRP remission, DAS28-ESR remission, SDAI remission, and CDAI remission at Week 24 (or Week 60)

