- How to account for ICEs: ICEs will be accounted using the same estimand strategy as for the primary estimand.
- Population-level summary: Proportion of participants achieving response at Week 24 (or Week 60) in each dosing regimen of peresolimab
- Rationale for estimand: Refer to the rationale for the primary estimand.

Secondary estimand for continuous endpoints at Week 24 and Week 60

For secondary objectives that have continuous endpoints analyzed at Week 12, the clinical question of interest is:

What is the average change from baseline to Week 24 (or Week 60) in the target patient population if all participants continued with treatment for 12 weeks without use of rescue or prohibited medications?

The estimand is described by the following attributes:

- Population: Participants with moderately-to-severely active RA
- Endpoint(s): Change from baseline for DAS28-hsCRP, SDAI, CDAI, TJC68, SJC66, and Physician's Global Assessment of Disease Activity (VAS) at Week 24 (or Week 60)

- How to account for ICEs: ICEs will be accounted using the same estimand strategy as for the secondary estimand for continuous endpoint at Week 12. It will be assumed that the same level of efficacy prior to the first ICE will continue, that is, last observation carried forward (LOCF) will be used for imputation.
- Population-level summary: Mean change from baseline to Week 24 in each intervention conditions
- Rationale for estimand: Refer to the rationale for the secondary estimand for continuous endpoints at Week 12.

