2.1. Multiplicity Adjustment

Adjustment for multiple comparisons will not be employed in the analysis for this study.

3. Analysis Sets

Abbreviations: CDAI = Clinical Disease Activity Index; LDA = low disease activity; Q4W = every 4 weeks; Q12W = every 12 weeks; SC = subcutaneous.

Table KDAF.3.1. Treatment Groups and Comparisons for Each Study Period and Analysis Population

Study Period	Analysis	Treatment Group	Abbreviation	Inferential
	Population			Comparison
Double-blind, placebo- controlled treatment period (Period 2)	mITT Population Safety Population	Placebo SC Q4W ^a Peresolimab 100 mg SC Q4W Peresolimab 400 mg SC Q4W Peresolimab 1000 mg SC Q4W	PBO PER100Q4W PER400Q4W PER1000Q4W	PER100Q4W vs. PBO PER400Q4W vs. PBO PER1000Q4W vs. PBO
Double-blind treatment period Weeks 12 to 24 (Period 3A)	Maintenance Population	Placebo SC Q4W to Peresolimab 400 mg SC Q4W Placebo SC Q4W to Peresolimab 1000 mg SC Q4W Peresolimab 100 mg SC Q4W Peresolimab 400 mg SC Q4W Peresolimab 1000 mg SC Q4W	PBO/PER400Q4W PBO/PER1000Q4W PER100Q4W PER400Q4W PER1000Q4W	No Between-Treatment Comparison
Double-blind treatment period Weeks 24 to 60 (Period 3B)	Maintenance Primary Population	Peresolimab 400 mg SC Q4W Peresolimab 400 mg SC Q12W Peresolimab 1000 mg SC Q4W Peresolimab 1000 mg SC Q12W	PER400Q4W PER400Q12W PER1000Q4W PER1000Q12W	No Between-Treatment Comparison
	Maintenance Secondary Population	Peresolimab 400 mg SC Q4W Peresolimab 1000 mg SC Q4W	PER400Q4W PER1000Q4W	No Between-Treatment Comparison
	Maintenance Tertiary Population	Placebo SC Q4W to Peresolimab 400 mg SC Q4W Placebo SC Q4W to Peresolimab 1000 mg SC Q4W Peresolimab 100 mg SC Q4W	PBO/PER400Q4W PBO/PER1000Q4W PER100Q4W	No Between-Treatment Comparison
Combined Periods 2 and 3A (Weeks 0 to 24)	mITT Population	Placebo SC Q4W to Peresolimab 400 mg SC Q4W Placebo SC Q4W to Peresolimab 1000 mg SC Q4W Peresolimab 100 mg SC Q4W Peresolimab 400 mg SC Q4W Peresolimab 400 mg SC Q4W Peresolimab 1000 mg SC Q4W	PBO/PER400Q4W PBO/PER1000Q4W PER100Q4W PER400Q4W PER1000Q4W	No Between-Treatment Comparison
Treatment Period (combined Periods 2 and 3; Weeks 0 to 60)	Safety Population (for exposure table)	Peresolimab 100 mg SC Q4W Peresolimab 400 mg SC Q4W Peresolimab 1000 mg SC Q4W	PER100Q4W PER400Q4W PER1000Q4W PER400Q4W/Q12W	No Between-Treatment Comparison

Study Period	Analysis	Treatment Group	Abbreviation	Inferential
	Population			Comparison
	Safety	Peresolimab 400 mg SC Q4W to Peresolimab 400 mg SC	PER1000Q4W/Q12W	

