Short Form-36 version 2 health survey acute form (SF-36v2)	The SF-36v2 Acute measure is a subjective, generic, health-related quality of life instrument that is patient-reported and consists of 36 questions covering 8 health domains: physical functioning, bodily pain, role limitations due to physical problems, role limitations due to emotional problems, general health perceptions, mental health, social function, and vitality. Each domain is scored by summing the individual items and transforming the scores into a 0 to 100 scale with higher scores indicating better health status or functioning. In addition, 2 summary scores, the physical component	 Physical Functioning Role Physical Bodily Pain General Health Vitality Social Functioning Role Emotional Mental Health 2 component Scores: MCS Score PCS Score 		
	score (PCS) and the mental component score (MCS), will be evaluated based on the 8 SF-36v2 Acute domains (McHorney et al. 1993; Ware et al. 2007; Ware and Sherbourne 1992; Maruish 2011).	Change from baseline in 8 associated domain scores and 2 component scores	Calculated as: Observed value – baseline value	Missing if baseline or observed value are missing.

Abbreviations: PGA = physician's global assessment; PatGA = patient's global assessment; RA = rheumatoid arthritis; SF-36 = Short Form-36 health survey acute form; SJC = swollen joint count; TJC = tender joint count.

Table KDAF.4.2. Description of Efficacy and Patient Reported Outcome Analyses

Measure	Variable	Estimand	Analysis Method	Population	Comparison and Timepoint	Analysis Type
American College of Rheumatology (ACR)	ACR20	Composite	Logistic with NRI	mITT	PER100Q4W vs. PBO; PER400Q4W vs. PBO; PER1000Q4W vs. PBO; At Week 12 and all other scheduled visits in Period 2	Primary analysis is at Week 12.
		Composite	Descriptive statistics with NRI	Maintenance	No between-treatment comparison; At Week 24 and all other scheduled visits in Period 3A	Secondary analysis is at Week 24.
		Composite	Descriptive statistics with NRI	Maintenance Primary; Maintenance Secondary; Maintenance Tertiary	No between-treatment comparison; At Week 60 and all other scheduled visits in Period 3B	Secondary analysis is at Week 60.
	ACR50/70	Composite	Logistic with NRI	mITT	PER100Q4W vs. PBO; PER400Q4W vs. PBO; PER1000Q4W vs. PBO; At Week 12 and all other scheduled visits in Period 2	Secondary analysis is at Week 12.

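### The Week 24 responder estimand covers the whole target population, but the visible Week 24 rows use a Period 3A set that may leave out Period 2 dropouts

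*SAP*

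**What the plan says.** SAP Section 1.1 poses the Week 24 categorical question as "What is the proportion of achieving a successful response at Week 24 (or Week 60) in the target patient population". To count as a success, the response must also have been reached "without use of rescue or prohibited medications or discontinuing the study intervention". The population attribute reads "Population: Participants with moderately-to-severely active RA", with no condition of having reached Week 12 or entered Period 3. For intercurrent events, "ICEs will be accounted using the same estimand strategy as for the primary estimand". The primary strategy is composite: "participants with ICEs related to study intervention will be considered as treatment failure (having no change from baseline), that is, a nonresponder". That status holds from the first such event onward, and early discontinuation from the study or from study intervention is on the list of events. The summary measure is "Population-level summary: Proportion of participants achieving response at Week 24 (or Week 60) in each dosing regimen of peresolimab".

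Table KDAF.4.2 (SAP Section 4.5) carries this out. Its Week 24 ACR20 row is composite, descriptive with nonresponder imputation (NRI), and timed as "No between-treatment comparison; At Week 24 and all other scheduled visits in Period 3A". Its population entry is Maintenance. The same entry appears in the Week 24 rows for ACR50/70 and for low disease activity and remission on DAS28-hsCRP, DAS28-ESR, SDAI and CDAI.

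Table KDAF.3.1 (SAP Section 3) ties the Maintenance Population to Period 3A, Weeks 12 to 24. A separate row in that table gives the mITT Population for Periods 2 and 3A combined, Weeks 0 to 24, with the same five regimens. No visible row of Table KDAF.4.2 uses that mITT set at Week 24. The text defining the Maintenance Population is not readable in the public document.

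**The concern.** A composite strategy works only if those who had the event stay in the denominator. NRI (SAP Section 4.1) acts on members of the analysis set and cannot bring back someone outside it. If the Maintenance Population starts with Period 3 entry, a participant who left the 400 mg arm at Week 8 is a nonresponder in the Week 12 mITT table and missing from the Week 24 table. The Week 24 figure then answers a different question: how often do those who got past Week 12 respond?

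Two readings of the results would suffer. Set beside the Week 12 mITT rate, the Week 24 rate could rise with no new responder. And in a study meant to choose dose and dosing frequency, an arm that loses more people early would look better at Week 24, although the composite strategy is there to count that loss against it.

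**Working it through.** **Inputs.** Arm sizes at Week 12 (SAP Section 5): about 60 at 100 mg, and about 120 each at 400 mg, 1000 mg and pooled placebo. They sum to 60 + 120 + 120 + 120 = 420, which reproduces the stated total. The documents give no Week 24 response rate and no Period 2 dropout rate. Protocol Section 7.2 says only that few discontinuations are expected. Both rates below are therefore assumptions, shown over a range.

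**Who is probably in the Maintenance Population.** This has to be inferred:

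- Table KDAF.3.1 lists Maintenance for Weeks 12 to 24 and mITT for Weeks 0 to 24 with the same five regimens. If Maintenance held everyone in mITT, the two sets would be redundant.
- SAP Section 4.6 uses the Safety Population for Period 2 safety data and changes to Maintenance for Period 3A.
- SAP Sections 4.1 and 4.6.2 take the safety baseline for later periods just before the first dose of that period. That fits a set of people dosed in Period 3A.

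**Size if only Period 3 entrants are included.** Let N be the mITT number in an arm, R the Week 24 responders, and x the share excluded. Under the composite strategy the excluded are all nonresponders, so R is the same either way:

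- rate matching the estimand: p = R/N
- rate as displayed: R/(N(1-x)) = p/(1-x)

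| True rate p | x = 3% | x = 5% | x = 10% | x = 15% |
|---|---|---|---|---|
| 30% | 30.9% (+0.9) | 31.6% (+1.6) | 33.3% (+3.3) | 35.3% (+5.3) |
| 40% | 41.2% (+1.2) | 42.1% (+2.1) | 44.4% (+4.4) | 47.1% (+7.1) |
| 50% | 51.5% (+1.5) | 52.6% (+2.6) | 55.6% (+5.6) | 58.8% (+8.8) |
| 60% | 61.9% (+1.9) | 63.2% (+3.2) | 66.7% (+6.7) | 70.6% (+10.6) |

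In counts, for an arm of 120 with 48 responders: 48/120 = 40.0%. With 6 excluded (5%), 48/114 = 42.1%. With 12 excluded (10%), 48/108 = 44.4%.

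**Unequal dropout.** Take two arms with the same true rate of 40%. One loses 3% in Period 2 and shows 41.2%; the other loses 10% and shows 44.4%. The 3.2-point gap comes from the denominator alone and favours the arm with more dropout.

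**Against sampling error.** At 40%, the 95% half-width is 1.96 × √(0.4 × 0.6/120) = 8.8 points for 120 participants and 1.96 × √(0.4 × 0.6/60) = 12.4 points for 60.

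**The case against.** The strongest case against is that the key fact sits in text we cannot read. A reader might infer outright that Period 2 dropouts leave the denominator and that Week 24 rates are inflated. The documents do not support that without a condition, because the Maintenance definition is not readable. This stands, and the conclusion is conditional for that reason.

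Nor does it follow that everyone who stops drug in Period 2 is excluded. Protocol Section 7.1 encourages those who stop study intervention to stay for the remaining visits. If membership depends on staying in the study, such people are in the set and count as nonresponders. So x is the share excluded, which may be smaller than the share who stopped drug.

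A reader might also extend the upward bias to all Week 24 rows. The continuous rows use a hypothetical strategy with LOCF. Discontinuation is not a failure there, and the direction of any bias is not fixed.

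The mITT Weeks 0 to 24 set may have been meant for this purpose, and Table KDAF.4.2 has lost some rows in the public copy. A missing row could be the answer, but the visible ACR block shows no obvious gap, and the visible rows that name Maintenance are the ones labelled as the secondary analysis at Week 24.

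On impact, Week 24 is descriptive with no between-treatment comparison, and no formal comparison of Week 12 with Week 24 is planned. If dropout is as low as the protocol expects, the shift is small beside sampling error. All of this stands and limits the importance of the point. It does not remove the mismatch: the shift is systematic and, for responder endpoints, always upward.

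**Conclusion.** The mismatch between estimand and analysis set is in the visible text: the Week 24 categorical estimand has no entry condition, and every visible row that implements it uses a set tied to Weeks 12 to 24.

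The consequence depends on one assumption, that the set holds only Period 3 entrants. That is a strong inference, not a documented fact. If it is right, Week 24 responder rates in the 100, 400 and 1000 mg arms are too high by 1/(1-x). At a true rate of 40% that is about 1 to 2 points for x of 3% to 5%, and 4.4 points at 10%. The ordering of doses is also open to distortion if early dropout differs between them.

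The claim covers the categorical Week 24 endpoints in the three arms on peresolimab from Week 0. It does not reach the Week 12 primary analysis (mITT), the continuous Week 24 rows, or the response-based sets used at Week 60. In the two placebo-start arms, those who left before Week 12 never received peresolimab, so counting them as failures of a peresolimab regimen would not be right either.

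**What to change.** First check the full Maintenance definition. If it requires Period 3 entry:

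- In Table KDAF.4.2, for the arms on 100, 400 and 1000 mg from Week 0, assign the Week 24 categorical secondary rows (ACR20/50/70; low disease activity and remission on all four indices) to the mITT set for Weeks 0 to 24 that Table KDAF.3.1 already contains, with composite strategy and NRI.
- Keep the Maintenance display for these arms as supportive.
- For the two placebo-start arms, keep Period 3 entrants, and state in Section 1.1 that the estimand population there is those who started peresolimab at Week 12.

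If the definition turns out to keep Period 2 dropouts, a sentence in Section 1.1 saying so settles the point.

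The cost is an SAP wording change, one extra display, and slightly less favourable Week 24 rates. No new data are needed.

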Participants randomly assigned to 400 mg or 1000 mg peresolimab at Week 0

Participants receiving 400 mg or 1000 mg peresolimab will continue their assigned dose and dosing frequency until Week 24. At Week 24, participants may be switched to every 12 weeks (Q12W) dosing following assessment of CDAI scores, unless they received rescue medication prior to Week 24.

Abbreviations: CDAI = Clinical Disease Activity Index; Q4W = every 4 weeks; Q12W = every 12 weeks.

- At Week 24 using the Visit 9 (Week 24) assessments, a participant does not achieve CDAI LDA
 - o These participants will receive permitted rescue therapy.
- For participants that achieved CDAI LDA at Week 24, those who do not maintain CDAI LDA for 2 consecutive visits after Week 24
 - o These participants will receive peresolimab Q4W and permitted rescue therapy.
 - If a participant is currently receiving peresolimab Q4W, they will continue receiving peresolimab Q4W.

• If a participant is currently receiving peresolimab Q12W, they will switch to peresolimab O4W.

[figure not shown]
Escape criteria after Week 24

A participant not achieving ≥20% improvement in both TJC and SJC at 2 consecutive visits after Week 24, while receiving rescue therapy, should be permanently discontinued from study intervention. Participants may continue in the study and receive additional standard of care therapies at the investigator's discretion.

Participation in an open-label extension study

If an open-label extension study is enrolling at the time the participant completes Visit 18 (Week 60), they will be given the opportunity to enroll in that study.

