1.2.1. Method of Assignment to Treatment

- 100 mg of peresolimab Q4W
- 400 mg of peresolimab Q4W
- 1000 mg of peresolimab Q4W
- placebo Q4W up to Week 12 followed by 400 mg of peresolimab Q4W, and
- placebo Q4W up to Week 12 followed by 1000 mg of peresolimab Q4W.

Participants who are randomized to either peresolimab 400 mg Q4W or peresolimab 1000 mg Q4W at Week 0 and meet CDAI \leq 10 at Week 24 will be randomly assigned to either Q4W or Q12W in the same dose level with a 1:1 ratio. Participants will be stratified by

• CDAI <2.8 vs 2.8 < CDAI <6 vs CDAI >6 at Week 24.

2. Statistical Hypotheses

The primary objective is to demonstrate that peresolimab is superior to placebo in achieving ACR20 at Week 12. Thus, the null hypothesis to be tested in relation to the primary estimand is:

There is no difference between peresolimab and placebo when evaluating the proportion of study participants with moderately-to-severely active RA achieving ACR20 at Week 12.

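### The visible Week 60 efficacy displays do not deliver the SAP's own Week 60 estimand for the arms randomised to 400 or 1000 mg, and their columns are not like for like with 100 mg

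*SAP*

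**What the plan says.** **Estimand (SAP Section 1.1, categorical endpoints at Weeks 24 and 60).** The clinical question opens "What is the proportion of achieving a successful response at Week 24 (or Week 60) in the target patient population". The population attribute reads "Population: Participants with moderately-to-severely active RA", and the summary measure is "Proportion of participants achieving response at Week 24 (or Week 60) in each dosing regimen of peresolimab". Nothing conditions on Week 24 status. Intercurrent events follow the primary estimand: a participant is a nonresponder after the first rescue or prohibited medication, or after stopping the study or study intervention early.

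**Design (Sections 1.2 and 1.2.1).** "Participants who are randomized to either peresolimab 400 mg Q4W or peresolimab 1000 mg Q4W at Week 0 and meet CDAI" of at most 10 "at Week 24 will be randomly assigned to either Q4W or Q12W in the same dose level with a 1:1 ratio". Section 1.2 adds that participants in these two arms may be switched "unless they received rescue medication prior to Week 24". The 100 mg arm stays on its regimen throughout, with no Week 24 split. Placebo participants move to 400 or 1000 mg at Week 12.

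**Analysis populations (Table KDAF.3.1, Weeks 24 to 60).**
- Primary: 400 and 1000 mg, each on Q4W and Q12W.
- Secondary: 400 and 1000 mg on Q4W only.
- Tertiary: 100 mg and the two placebo-switch groups.

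The mITT population is listed for Period 2 and for Weeks 0 to 24. The Weeks 0 to 60 row lists safety populations only.

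**Analyses (Table KDAF.4.2).** Each visible Week 60 row names "Maintenance Primary; Maintenance Secondary; Maintenance Tertiary" as the population and states "No between-treatment comparison; At Week 60 and all other scheduled visits in Period 3B". For safety, Section 4.6 pools the Period 3B groups across the three sets. No such statement appears for efficacy.

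**The concern.** The estimand describes one unconditional population. The planned rows appear to describe three subsets that are formed differently by dose. For participants randomised at Week 0 to 400 or 1000 mg, the label PER400Q4W or PER1000Q4W appears once for people who met the Week 24 CDAI criterion and again for people who did not go on to re-randomisation. PER100Q4W appears once and mixes both kinds. Participants who stopped before Week 24, whom the estimand counts as nonresponders, probably appear in none of the three sets.

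The study is meant to inform dose and dosing frequency. If the Week 60 tables are produced as planned, the quantity that the SAP defines is not reported for the two higher-dose arms, and the columns that look like a dose comparison differ through selection at Week 24.

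**Working it through.** **Step 1: stated group sizes.** SAP Section 5 gives 60 (100 mg), 120 (400 mg), 120 (1000 mg) and 120 (placebo). 60 + 120 + 120 + 120 = 420, which matches the stated total. The documents give no Week 60 figure to reproduce.

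**Step 2: estimand against display.**

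| Element | Week 60 estimand | Visible Week 60 rows |
|---|---|---|
| Population | All with moderately-to-severely active RA | Three sets that begin at Week 24 |
| 400 and 1000 mg arms from Week 0 | One proportion per regimen | Divided between Primary and Secondary |
| 100 mg arm | One proportion | One undivided column in Tertiary |
| Lost before Week 24 | Nonresponder | Probably not in the denominator |

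The Section 3 set definitions are not in the public text. The right-hand column is inferred from Sections 1.2 and 1.2.1 and from the groups in Table KDAF.3.1: Q12W occurs only in Primary, and only re-randomised participants can receive it. The Version 3 change log agrees that the Weeks 0 to 60 row is for safety: it records that mITT was taken out of that row.

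**Step 3: size of the selection effect for responder endpoints.** None of these inputs comes from the documents. All are assumed, and all are set equal across doses so that the true dose difference is zero.
- q = share with CDAI of at most 10 and no rescue at Week 24: 0.20 to 0.50
- m = Week 60 response rate in that group: 0.60 to 0.80
- s = Week 60 response rate in the others: 0, 0.1 or 0.3
- r = retention to Week 24: 0.8 to 1.0

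Displayed rates: Primary = m; Secondary = s; 100 mg in Tertiary = q·m + (1 − q)·s.

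Apparent gap, Primary minus 100 mg = (1 − q)(m − s).

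| s | Smallest gap (q = 0.5, m = 0.6) | Largest gap (q = 0.2, m = 0.8) |
|---|---|---|
| 0 | 0.5 × 0.6 = 30 points | 0.8 × 0.8 = 64 points |
| 0.1 | 0.5 × 0.5 = 25 points | 0.8 × 0.7 = 56 points |
| 0.3 | 0.5 × 0.3 = 15 points | 0.8 × 0.5 = 40 points |

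The value s = 0 reflects the rescue rule in Section 1.2 for participants not in CDAI low disease activity at Week 24, combined with the composite strategy. It is assumed to act alike in every arm.

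**Step 4: the estimand on the same inputs.** All-randomised rate = r·[q·m + (1 − q)·s], identical at every dose. With s = 0 it runs from 0.8 × 0.2 × 0.6 = 9.6% to 1.0 × 0.5 × 0.8 = 40%.

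**Step 5: one case in counts (q = 0.35, r = 0.9, m = 0.8, s = 0).**
- 400 mg: 120 × 0.9 = 108 reach Week 24. 108 × 0.35 = 37.8 enter Primary, 18.9 per schedule, and 70.2 enter Secondary.
- 100 mg: 60 × 0.9 = 54, undivided.
- Displayed: Primary 80%, Secondary 0%, 100 mg 0.35 × 0.8 = 28%.
- Primary and Secondary pooled by hand for 400 mg: 37.8 × 0.8 / 108 = 28%, equal to 100 mg, as it should be.
- All randomised: 30.24 / 120 = 25.2% for 400 mg and 15.12 / 60 = 25.2% for 100 mg.

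Pooling removes the false gap but keeps the wrong denominator: 28% against 25.2%.

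**The case against.** The strongest reply is that these are descriptive secondary summaries with no planned between-treatment comparison. Dose-response modelling is planned on the primary endpoint and, if needed, on other core efficacy endpoints. All five arms are shown undivided at Week 24 in the Maintenance population, and the randomised Q4W and Q12W columns within Primary address dosing frequency. A reader who respects the population names will not compare across them. All of this is true and limits the harm. It does not close the gap, because the estimand is itself a single-arm proportion and no visible row plans it for the two higher-dose arms. Hand pooling mixes Q4W with Q12W, and participants lost before Week 24 would probably still be left out.

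Four further limits stand.
- The set definitions are inferred.
- Parts of Table KDAF.4.2 are redacted, so a reader might infer that no all-randomised Week 60 display exists, but the text supports only that none is visible.
- A reader might infer that every 400 and 1000 mg column is response-selected. Tertiary holds placebo-to-400 and placebo-to-1000 mg groups that appear unselected, although their 48 weeks on drug after 12 weeks of placebo do not match 60 weeks on 100 mg.
- The arithmetic covers responder endpoints only. Continuous Week 60 endpoints use a hypothetical strategy with LOCF, so the gap figures cannot be carried over to them.

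**Conclusion.** The mismatch between the Week 60 estimand and its visible displays is real, and the SAP should correct it. For the arms randomised at Week 0 to 400 or 1000 mg, no visible display gives the stated Week 60 proportion. Their Primary and Secondary columns are not comparable with PER100Q4W.

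With equal true effects, the responder gap between Primary and 100 mg is about 30 to 64 points when Week 24 nonresponders all count as Week 60 nonresponders, and 15 to 40 points when 30% of them respond. These figures show how large selection alone could be. They do not estimate a bias in this trial, since every input is assumed.

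A reader might go further and infer that the plan makes a biased dose comparison or that its main result is compromised. The documents do not support this: no Week 60 comparison is planned, the Week 12 primary analysis in mITT is unaffected, and the Q4W and Q12W columns within Primary rest on their own 1:1 randomisation.

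**What to change.** Add to Tables KDAF.3.1 and KDAF.4.2 a descriptive Week 60 responder row in the mITT population by arm randomised at Week 0. Apply the stated composite strategy and NRI to everyone, including participants lost before Week 24. State that the 400 and 1000 mg figures average over the Week 24 re-randomisation to Q4W or Q12W. Label the Primary and Secondary displays as conditional on Week 24 status, and keep them as the maintenance results.

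Two additions are optional:
- Schedule-specific estimates for 400 and 1000 mg, useful if regimen is meant to include the schedule after Week 24. Re-randomised participants on the schedule of interest get weight 2 (from the 1:1 ratio) and those never re-randomised get weight 1. In the case worked above, 2 × 18.9 + 70.2 = 108, which recovers everyone who reached Week 24; those lost earlier are added as nonresponders.
- A split of the Tertiary columns by the same Week 24 status, so that subsets can be read like for like.

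The cost is SAP wording and extra table programming on data already collected. Standard errors are wider only if the weighted version is used.
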